Appendix 5. West Haven Criteria

<http://www.mdcalc.com/hepatic-encephalopathy-grades-stages/>

| Grade of Hepatic Encephalopathy | Description | Suggested Operative Criteria |
|---------------------------------|---|---|
| Grade I | 
• Trivial lack of awareness• Euphoria or anxiety• Shortened attention span• Impairment of addition or subtraction• Altered sleep rhythm | Despite oriented in time and space (see below), the patient appears to have some cognitive/ behavioral decay with respect to his or her standard on clinical examination or to the caregivers |
| Grade II | 
• Lethargy or apathy• Disorientation for time• Obvious personality change• Inappropriate behavior• Dyspraxia• Asterixis | Disoriented for time (at least three of the followings are wrong: day of the month, day of the week, month, season, or year) ± the other mentioned symptoms |
| Grade III | 
• Somnolence to semistupor• Responsive to stimuli• Confused• Gross disorientation• Bizarre behavior | Disoriented also for space (at least three of the following wrongly reported: country, state [or region], city, or place) ± the other mentioned symptoms |
| Grade IV | 
• Coma | Does not respond even to painful stimuli |

Adapted from {Vilstrup 2014}

Appendix 6. IBD Symptom Severity Assessment

| | |
|-------------------------------|---|
| Bleeding History ¹ |  0 no recent bleeding  1 rare, minimal blood  2 blood in some stools  3 blood in most stools, or blood alone in any stool |
| Daily Bowel Movement Count |  0 no change from a typical day  1 < 3 more stools than on a typical day  2 3-5 more stools than on a typical day  3 > 5 more stools than on a typical day |

1 Does not include history of perianal bleeding

ULN	upper limit of normal
VAS	visual analog scale
WHO	World Health Organization

PHARMACOKINETIC ABBREVIATIONS

AUC_{last}	area under the concentration versus time curve from time zero to the last quantifiable concentration
AUC_{tau}	area under the concentration versus time curve over the dosing interval
C_{last}	last observed quantifiable concentration of the drug
C_{max}	maximum observed concentration of drug
C_{tau}	observed drug concentration at the end of the dosing interval
CL_{ss}/F	apparent oral clearance after administration of the drug: at steady state: $CL_{ss}/F = Dose/AUC_{tau}$, where “Dose” is the dose of the drug
$t_{1/2}$	estimate of the terminal elimination half-life of the drug, calculated by dividing the natural log of 2 by the terminal elimination rate constant (λ_z)
T_{last}	time (observed time point) of C_{last}
T_{max}	time (observed time point) of C_{max}
λ_z	terminal elimination rate constant, estimated by linear regression of the terminal elimination phase of the concentration of drug versus time curve

1. INTRODUCTION

This statistical analysis plan (SAP) describes the statistical analysis methods and data presentations to be used in tables, figures, and listings (TFLs) in the clinical study report (CSR) for Study GS-US-428-5443. This SAP is based on the study protocol amendment 3 dated 15 January 2021 and the electronic case report form (eCRF). The SAP will be finalized before database finalization. Any changes made after the finalization of the SAP will be documented in the CSR.

The study enrollment was terminated early by the sponsor on 30 July 2021 due to recruitment challenges in a rare disease population.

1.1. Study Objectives

The primary objective of this study is as follows:

- To assess the safety and tolerability of escalating doses of cilofexor (CILO, previously known as GS-9674) in subjects with primary sclerosing cholangitis (PSC) and compensated cirrhosis

CCI

[figure not shown]

1.2. Study Design

This is a proof of concept, open-label study evaluating the safety and tolerability of CILO in subjects with PSC and compensated cirrhosis.

Eligible subjects were enrolled and received treatment with escalating doses of CILO over 12 weeks. Subjects dose escalated at Week 4 (from 30 mg to 60 mg once daily) and Week 8 (from 60 mg to 100 mg once daily) if in the opinion of the Principal Investigator (PI) study drug had been tolerated.

The overall study design is presented graphically in the figure below.

Individual subject participation in the study can last up to 20 weeks, which includes a 4-week screening period, a 12-week treatment period (divided into three 4-week dosing stages at 30 mg QD, 60 mg QD, and 100 mg QD), and a Follow-Up visit 4 weeks after the Week 12 visit.

Study drug dosing may be interrupted for up to 4 consecutive weeks at the discretion of the PI if a subject experienced an adverse event (AE) (eg, intolerable pruritus) thought to be related to the study drug. During the period of study drug dose interruption, subjects were not required to attend in-clinic visits per the Study Procedures Table ([Appendix 1](#)) but were monitored via weekly telephone follow-up visits (refer to Section 7.5.5 of study protocol). If a study drug dose interruption required reinitiation of a dosing stage, participation in the study could be extended from up to 20 weeks to up to 28 weeks to complete 4 consecutive weeks of dosing at each dose stage.

1.3. Sample Size and Power

Due to the exploratory nature of this study, no formal power calculations were used to determine sample size.

2. TYPE OF PLANNED ANALYSIS

2.1. Interim Analyses

No interim analysis for efficacy was planned.

2.1.1. Data Monitoring Committee Analyses

This study had an internal multidisciplinary Data Monitoring Committee (DMC) to review the progress of the study and safety of the study after 10 subjects completed 4 weeks of CILO 30 mg treatment.

The DMC's role and responsibilities and the scope of analysis provided to the DMC were provided in a mutually agreed upon charter, which defines the DMC membership, meeting logistics, and meeting frequency.

2.2. Final Analysis

The final analysis will be performed after all subjects have completed the study, outstanding data queries have been resolved or adjudicated as unresolvable, and the data have been cleaned and finalized.

2.3. Changes from Protocol-Specified Analysis

Due to limited subject enrollment in the study, part of safety summaries and listings (body weight, vital signs, prior and concomitant medications, electrocardiogram [ECG], and pharmacodynamic parameters) planned in the protocol will not be provided.

PSC Patient-Reported Outcome (PRO) is a novel endpoint. CCI [REDACTED]

3. GENERAL CONSIDERATIONS FOR DATA ANALYSES

Analysis results will be presented using descriptive statistics. For categorical variables, the number and percentage of subjects in each category will be presented; for continuous variables, the number of subjects (n), mean, standard deviation (SD) or standard error (SE), median, first quartile (Q1), third quartile (Q3), minimum, and maximum will be presented.

By-subject listings will be presented for all subjects in the All Enrolled Analysis Set, and sorted by subject identification (ID) number in ascending order, visit date, and time (if applicable), unless otherwise specified. Data collected on log forms, such as AEs, will be presented in chronological order within subject. Age, sex at birth, race, and ethnicity will be included in the listings, as space permits.

3.1. Analysis Sets

Analysis sets define the subjects to be included in an analysis. Analysis sets and their definitions are provided in this section. The analysis set will be identified and included as a subtitle of each table, figure, and listing.

For each analysis set, the number and percentage of subjects eligible for inclusion will be provided in the disposition table as detailed in Section 4.

3.1.1. All Enrolled Analysis Set

All Enrolled Analysis Set includes all subjects who received a study subject identification number in the study after screening.

3.1.2. Safety Analysis Set

The Safety Analysis Set includes all subjects who took at least 1 dose of study drug. This is the primary analysis set for safety analyses.

3.1.3. Pharmacokinetic Analysis Sets

The Pharmacokinetic (PK) Analysis Sets will include all enrolled subjects who took at least 1 dose of study drug and have at least 1 nonmissing concentration value reported by the PK laboratory for the corresponding analytes. These are the primary analysis sets for all PK analyses.

CCI

3.1.5. Pharmacodynamic Analysis Sets

The Pharmacodynamic (PD) Analysis Sets will include all enrolled subjects who received at least 1 dose of study drug and have at least 1 nonmissing PD value for each respective PD parameter.

CCI [REDACTED]
[REDACTED]
[REDACTED]

3.2. Strata and Covariates

This study did not use a stratified randomization schedule when enrolling subjects. No covariates will be included in efficacy and safety analyses.

3.3. Examination of Subject Subgroups

There are no prespecified subject subgroupings for analyses.

3.4. Multiple Comparisons

Adjustments for multiplicity will not be made, because no formal statistical testing will be performed in this study.

3.5. Missing Data and Outliers

3.5.1. Missing Data

In general, missing data will not be imputed unless methods for handling missing data are specified. Exceptions are presented in this document.

For missing last dosing date of study drug, imputation rules are described in Section 4.2. The handling of missing or incomplete dates for AE onset is described in Section 7.1.5.2.

3.5.2. Outliers

Outliers of non-PK data will be identified during the data management and data analysis process, but no sensitivity analyses will be conducted. All data will be included in the data analysis.

3.6. Data Handling Conventions and Transformations

The following conventions will be used for the imputation of date of birth when it is partially missing or not collected:

- If only month and year of birth is collected, then “15” will be imputed as the day of birth.

- If only year of birth is collected, then “01 July” will be imputed as the day and month of birth.
- If year of birth is missing, then date of birth will not be imputed.

In general, age collected at Day 1 (in years) will be used for analyses and presented in listings. If age at Day 1 is not available for a subject, then age derived based on date of birth and the Day 1 visit date will be used instead. If an enrolled subject was not dosed with any study drug, the enrollment date will be used instead of the Day 1 visit date. For screen failures, the date the first informed consent was signed will be used for the age derivation. Age required for longitudinal and temporal calculations and analyses (eg, estimates of creatinine clearance, age at date of AE) will be based on age derived from date of birth and the date of the measurement or event, unless otherwise specified.

Non-PK data that are continuous in nature but are less than the lower limit of quantitation (LOQ) or above the upper LOQ will be imputed as follows:

- A value that is 1 unit less than the lower LOQ at the same precision level of the originally reported value will be used to calculate descriptive statistics if the datum is reported in the form of “ $< x$ ” (where x is considered the lower LOQ). For example, if the values are reported as < 50 and < 5.0 , values of 49 and 4.9, respectively, will be used to calculate summary statistics. An exception to this rule is any value reported as < 1 or < 0.1 , etc. For values reported as < 1 or < 0.1 , a value of 0.9 or 0.09, respectively, will be used to calculate summary statistics.
- A value that is 1 unit above the upper LOQ will be used to calculate descriptive statistics if the datum is reported in the form of “ $> x$ ” (where x is considered the upper LOQ). Values with decimal points will follow the same logic as the bullet point above.
- The lower or upper LOQ will be used to calculate descriptive statistics if the datum is reported in the form of “ $\leq x$ ” or “ $\geq x$ ” (where x is considered the lower or upper LOQ).

If methods based on the assumption that the data are normally distributed are not adequate, analyses may be performed on transformed data or nonparametric analysis methods may be used, as appropriate.

Natural logarithm transformation will be used for analyzing concentrations and PK parameters in intensive PK samples, if applicable. Concentration values that are below the limit of quantitation (BLQ) will be presented as “BLQ” in the concentration data listing. Values that are BLQ will be treated as 0 at predose time points, and one-half the value of the LOQ at postdose time points for summary purposes.

The following conventions will be used for the presentation of summary and order statistics:

- If at least 1 subject has a concentration value of BLQ for the time point, the minimum value will be displayed as “BLQ.”

- If more than 25% of the subjects have a concentration data value of BLQ for a given time point, the minimum and Q1 values will be displayed as “BLQ.”
- If more than 50% of the subjects have a concentration data value of BLQ for a given time point, the minimum, Q1, and median values will be displayed as “BLQ.”
- If more than 75% of the subjects have a concentration data value of BLQ for a given time point, the minimum, Q1, median, and Q3 values will be displayed as “BLQ.”
- If all subjects have concentration data values of BLQ for a given time point, all order statistics (minimum, Q1, median, Q3, and maximum) and summary statistics will be displayed as “BLQ.”

PK parameters that are BLQ will be imputed as one-half LOQ before log transformation or statistical model fitting, if applicable.

3.7. Analysis Visit Windows

3.7.1. Definition of Study Day

Study day will be calculated from the first dosing date of study drug and derived as follows:

- For postdose study days: Assessment Date – First Dosing Date + 1
- For days prior to the first dose: Assessment Date – First Dosing Date

Therefore, study Day 1 is the day of first dose of study drug administration.

Additional calculations for subjects who require a PI-approved study drug interruption are as follows. Post-interruption study day will be calculated from the first dosing date of study drug subsequent to post-interruption and derived as follows:

- For post-interruption dosing resumed from 30 mg: Assessment Date – First Post-interruption Dosing Date + 1
- For post-interruption dosing resumed from 60 mg: Assessment Date – First Post-interruption Dosing Date + 29
- For post-interruption dosing resumed from 100 mg: Assessment Date – First Post-interruption Dosing Date + 57

Therefore, the day of first post-interruption dose of study drug administration can be Post-interruption study Day 1, 29, or 57, depending on the dose level when PI-approved study drug dose interruption occurs.

3.7.2. Analysis Visit Windows

Subject visits might not occur on protocol-specified days. Therefore, for the purpose of analysis, observations will be assigned to analysis windows.

On-treatment visit windows will be calculated from study Day 1 or the first post-interruption study drug dosing date for selected efficacy measures, elastography, and safety laboratory data.

Selected safety and efficacy data, unless otherwise specified, collected up to and including the last dosing date + 30 days, will be mapped according to the following analysis windows unless the nominal visit name is early termination (ET) or Follow-Up.

The analysis windows for selected measures are provided in [Table 3-1](#) to [Table 3-3](#). The algorithm for assigning baseline analysis window does not apply to the liver tests (ALP, total bilirubin, ALT, AST, and GGT). For these 5 parameters, the baseline values will be determined by averaging the values obtained at Screening and Baseline/Day 1, and no specific study day is associated with the average values.

Table 3-1. Analysis Visit Windows for Chemistry, eGFR, Hematology, Coagulation, Child-Pugh (CP)/ Model for End-stage Liver Disease (MELD) Scores, Pruritus VAS, 5D-Itch and Biomarkers, Including hsCRP, ELF™ Score and Components, FibroSURE/FibroTest® and Selected Components, Bile Acids, FGF19, C4.

Nominal Visit	Nominal Study Day/Post-interruption Study Day	Visit Window Study Day/Post-interruption Study Day	
		Lower Limit	Upper Limit
Baseline/Post-interruption Day 1	1	(none)	1
Week 1/Post-interruption Week 1	8	2	18
Week 4/Post-interruption Week 4	29	19	42
Week 8/Post-interruption Week 8	57	43	70
Week 12/Post-interruption Week 12	85	71	≥85

Table 3-2. Analysis Visit Windows for IBD Symptoms

Nominal Visit	Nominal Study Day/Post-interruption Study Day	Visit Window Study Day/Post-interruption Study Day	
		Lower Limit	Upper Limit
Baseline/Post-interruption Day 1	1	(none)	1
Week 4/Post-interruption Week 4	29	2	42
Week 8/Post-interruption Week 8	57	43	70
Week 12/Post-interruption Week 12	85	71	≥85

Table 3-3. Analysis Visit Windows for QoL Questionnaires and FibroScan

Nominal Visit	Nominal Study Day/Post-interruption Study Day	Visit Window Study Day/Post-interruption Study Day	
		Lower Limit	Upper Limit
Baseline/Post-interruption Day 1	1	(none)	1
Week 12/Post-interruption Week 12	85	2	≥ 85

Data relating to unscheduled visits may be assigned to a particular visit or time point based on the visit windows. The following conventions will be followed:

- An unscheduled visit prior to the first dosing of study drug may be included in the calculation of the baseline value, if applicable.
- Unscheduled visits after the first dose of study drug will be included in determining the maximum postbaseline toxicity grade.
- For subjects who prematurely discontinue from the study, early termination (ET) data will be summarized as a separate visit, labeled as “Early Termination Visit.”
- Data collected on a follow-up visit will be summarized as a separate visit and labeled “Follow-up Visit.”
- Data obtained after the follow-up visit or last dose date plus 30 days (whichever is later) will be excluded from the summaries but will be included in the listings.

3.7.3. Selection of Data in the Event of Multiple Records in an Analysis Visit Window

Depending on the statistical analysis method, single values may be required for each analysis window. For example, change from baseline by visit usually requires a single value, whereas a time-to-event analysis would not require 1 value per analysis window.

If multiple valid, nonmissing measurements exist in an analysis window, records will be chosen based on the following rules if a single value is needed:

- For baseline, the last nonmissing value on or prior to the first dosing date of study drug will be selected, unless specified differently. If there are multiple records with the same time or no time recorded on the same day, the baseline value will be the average of the measurements for continuous data, or the measurement with the lowest severity for categorical data.

- For each liver test (ALP, total bilirubin, ALT, AST, and GGT), the baseline value will be determined by averaging all values obtained between Screening and Baseline/Day 1 (inclusive). The corresponding baseline reference range will be defined as the one associated with the latest visit that was included for computing the baseline value, for the purpose of determination of the abnormality and/or toxicity grades.
- For postbaseline values:
 - The record closest to the nominal day for that visit will be selected.
 - If there are 2 or more records that are equidistant from the nominal day, the later record will be selected.
 - If there is more than 1 record on the selected day, the average will be taken for continuous data and the worst severity will be taken for categorical data, unless otherwise specified.
 - FGF19 and C4 obtained on the same day will not be averaged. The predose value would be selected to represent the study visit, when the data are summarized by study visit and not by timepoint within a visit. The summary by timepoint is described separately in Section 9.3.

Liver stiffness by transient elastography data in each analysis visit window will be chosen based on the following rules:

- For baseline, measurements by M probe will be selected for analysis if available, otherwise measurements by XL probe will be selected.
- For postbaseline visits, measurements by the same probe type (XL or M) selected for the subject at baseline will be selected in each analysis visit window. If no measurement by the same probe type as baseline is available, the analysis value for the corresponding postbaseline visit will be considered missing. If there are multiple postbaseline records by the same probe type as baseline, the rules to choose postbaseline continuous measurements as described above will apply.

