1.4. Rationale for Dose Selection of CILO

In this study we aim to evaluate the safety and tolerability of escalating daily doses of CILO from 30 to 100 mg once daily in a PSC population with compensated cirrhosis.

A dose of CILO 100 mg daily provided greater therapeutic benefit than a dose of CILO 30 mg in a Phase 2 study in subjects with PSC without cirrhosis (Study GS-US-428-4025). Subjects with compensated cirrhosis are expected to have approximately 1.8-fold higher CILO plasma exposure compared to those without cirrhosis (GS-US-402-3885; Section [1.2.6](#)). CILO is a hepatic OATP substrate, and the higher CILO plasma exposure observed in subjects with compensated cirrhosis is attributable to decreases in hepatic uptake by OATP, and not expected to alter the hepatic exposure of CILO. Thus, a similar dose of CILO 100 mg is expected to be needed for efficacy in subjects with PSC and compensated cirrhosis. Adequate exposure margins (5- to 11-fold relative to preclinical NOAEL exposures) are expected after 100 mg CILO administration in subjects with PSC and compensated cirrhosis.

The current study is designed to assess the safety of increasing daily doses of CILO from 30 to 100 mg daily in subjects with PSC and compensated cirrhosis. The starting dose, CILO 30 mg once daily, was well tolerated following 12 weeks of treatment in subjects with compensated cirrhosis due to NASH (GS-US-384-3914) and conferred improvements in liver biochemistry (eg, GGT) and markers of cholestasis (eg, C4) in patients with noncirrhotic PSC (GS-US-428-4025). After 4 weeks of dosing with CILO 30 mg, the dose will escalate to 60 mg and then to 100 mg over 4-week intervals, to evaluate the safety, tolerability and improvements in ALP and other liver biochemistry tests at each dose level in subjects with PSC and compensated cirrhosis.

Dosing of CILO in this study will be without regard to food based on PK, PD, safety and efficacy data from Phase 1 studies in healthy subjects and subjects with hepatic impairment (GS-US-402-1851, GS-US-454-4315, and GS-US-402-3885) and Phase 2 studies in subjects with NASH with or without cirrhosis (GS-US-402-1852 and GS-US-384-3914).

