3. STUDY DESIGN

3.1. Study Design

[figure not shown]
This is a proof of concept, open-label study evaluating the safety and tolerability of CILO in subjects with PSC and compensated cirrhosis.

Eligible subjects will be enrolled and receive treatment with escalating doses of CILO over 12 weeks. Subjects will dose escalate at Week 4 (from 30 mg to 60 mg once daily) and Week 8 (from 60 mg to 100 mg once daily) if in the opinion of the principal investigator (PI) study drug is being tolerated.

Individual subject participation in the study can last up to 20 weeks, which includes a 4-week screening period, a 12-week treatment period (divided into three 4-week dosing stages at 30 mg QD, 60 mg QD, and 100 mg QD), and a follow-up visit 4 weeks after the Week 12 visit.

Study drug dosing may be interrupted for up to 4 consecutive weeks at the discretion of the PI if a subject experiences an AE (eg, intolerable pruritus) thought to be related to the study drug. During the period of study drug dose interruption, subjects are not required to attend in-clinic visits per the Study Procedures Table ([Appendix 2](#)) but will be monitored via weekly telephone follow-up visits (refer to Section [7.5.5](#)). If a study drug dose interruption requires reinitiation of a dosing stage, participation in the study could be extended from up to 20 weeks to up to 28 weeks to complete 4 consecutive weeks of dosing at each dose stage.

The overall study design is shown in the figure below:

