6.4. Treatment Assessments

6.4.1. Week 1, Week 4, Week 8, and Week 12 (\pm 3 days)

Subjects should be instructed to fast (no food or drink, except water), starting from midnight (00:00) or earlier, as appropriate, on the evening prior to ensure an approximate 8-hour fast prior to the fasted blood sample collection the next morning.

Subjects should also be instructed to HOLD their dose of study drug on the day of their visit until all blood sample collections have been completed.

The following treatment procedures/assessments are to be completed and documented at these in-clinic visits:

- For subjects with history of IBD (as appropriate, see Section 6.8.6):

IBD symptom severity assessment (Week 4, Week 8, and Week 12)

any evidence of active IBD seen on routinely performed colonoscopy will be captured at all in-clinic visits

- Symptom-driven physical examination including ascites and HE assessments
- Record vital signs and body weight
- Obtain blood samples for:

Chemistry

eGFR

Hematology

Coagulation Panel

Lipid Profile (Week 4, Week 8, and Week 12)

C-peptide, Insulin and HbA_{1c} (Week 12)

Biomarkers (Week 1, Week 4, Week 8, and Week 12)

cc1 [REDACTED]
[REDACTED]
[REDACTED]
[REDACTED]

The date and time of the previous study drug dose will need to be documented

cc1 [REDACTED]

- CP and MELD scores
- Obtain urine samples for:

Urine pregnancy testing for females of childbearing potential only at Week 4, 8, and 12

- Collect stool sample (Week 12) for bile acids by mass spectrometry (if available)
- Perform FibroScan at Week 12
- Record all CMs that the subject has taken since the previous visit
- Record any SAEs and all AEs occurring since the previous visit
- Dispense the study drug as directed by IWRS (Week 4 and Week 8)
- Review study drug compliance and study drug administration instructions with subject

Reconcile study drug administration using pill counts

In the case of a PI approved study drug dose interruption, subjects will have weekly telephone follow-up assessments as detailed in Section 6.4.2. During the study drug dose interruption, subjects are otherwise not required to complete in-clinic assessments unless deemed necessary given the rationale for their study drug dose interruption (eg, Close Observation for drug-induced liver injury [DILI], follow up of non-DILI laboratory abnormalities).

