Treatment-emergent toxicities will be noted by the investigator and brought to the attention of the medical monitor. Whether or not considered treatment-related, all subjects experiencing AEs must be monitored periodically until symptoms subside, any abnormal laboratory values have resolved or returned to baseline levels or they are considered irreversible, or until there is a satisfactory explanation for the changes observed.

Other than in the case of the liver enzymes noted above, Grade 3 or 4 clinically significant laboratory abnormalities should be confirmed by repeat testing within 48-72 hours of results, and preferably within 3 calendar days of receipt of the original test results. For AEs associated with laboratory abnormalities, the event should be graded on the basis of the clinical severity in the context of the underlying conditions; this may or may not be in agreement with the grading of the laboratory abnormality.

Any questions regarding toxicity management should be directed to the medical monitor.

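### The SAP's Week 4 and Week 8 windows ignore dose escalation, so a sample taken on the next dose can stand as the end-of-stage value in by-visit summaries

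*SAP*

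**What the plan says.** Protocol 3.1 ties the dose change to the visit: "Subjects will dose escalate at Week 4 (from 30 mg to 60 mg once daily) and Week 8". Protocol 6.4.1 has subjects hold that day's dose until blood is drawn, and then gives the site this step: "Dispense the study drug as directed by IWRS (Week 4 and Week 8". The scheduled sample is therefore the last one on the old dose. Protocol 1.4 gives the purpose of the stages: "to evaluate the safety, tolerability and improvements in ALP and other liver biochemistry tests at each dose level".

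SAP 3.7.2 puts records into windows by study day: "Therefore, for the purpose of analysis, observations will be assigned to analysis windows". The Table 3-1 rows (nominal day, lower limit, upper limit) are "Week 4/Post-interruption Week 4 29 19 42" and "Week 8/Post-interruption Week 8 57 43 70". Unscheduled visits may be placed in these windows; only early-termination and follow-up visits are exempt.

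Where one value is needed, SAP 3.7.3 takes the record nearest the nominal day. For ties: "If there are 2 or more records that are equidistant from the nominal day, the later record will be selected".

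The protocol plans repeat tests. For non-liver Grade 3 or 4 clinically significant laboratory abnormalities, Protocol 7.5.2 says they "should be confirmed by repeat testing within 48-72 hours of results". Section 7.5.1 sets the same interval for on-treatment liver elevations, and 7.5.3 for a Child-Pugh score of 7 or more.

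**The concern.** Selection depends on calendar distance alone. Nothing in the visible text considers the dose level, the date of escalation, or whether a record was scheduled. After an early visit, a repeat drawn on the next dose can lie as near to the nominal day as the scheduled sample, or nearer, and it is then the one selected.

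The visible SAP has no tabulation by dose, so visit is the only readable link to dose: Week 4 for 30 mg and Week 8 for 60 mg. A substituted value blurs that link. The substitution is also selective, because an abnormal end-of-stage result is what prompts the repeat. Enrollment was stopped early (SAP 1), so a single value can move a by-visit summary.

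**Working it through.** **Inputs.** Nominal days 8, 29, 57 and 85 and their windows (SAP Table 3-1). Visit allowance of 3 days either way (Protocol 6.4.1), which puts Week 4 on Days 26–32 and Week 8 on Days 54–60. Repeat 48–72 hours after results, taken as 2 or 3 days (Protocol 7.5.1–7.5.3). Laboratory turnaround is not given; 0 to 3 days is assumed, so the gap from visit to repeat is 2 to 6 days.

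**1. Reproduce the windows.** They are midpoints between nominal days:
- (8 + 29)/2 = 18.5, giving limits 18 and 19
- (29 + 57)/2 = 43, giving 42 and 43
- (57 + 85)/2 = 71, giving 70 and 71

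All match Table 3-1.

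**2. Overrun into the next stage.** 42 − 29 = 13 days and 70 − 57 = 13 days for an on-time visit. At Week 4, a visit 3 days early gives 42 − 26 = 16 days and one 3 days late gives 42 − 32 = 10.

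**3. When a repeat displaces the scheduled record.** Let d be the visit offset from the nominal day and g > 0 the gap to the repeat. The repeat is selected when |d + g| ≤ |d|, that is, when d < 0 and g ≤ 2|d|. If escalation waits until the nominal day, the repeat is on the new dose only if also d + g > 0; a sample on the nominal day itself is predose, because Protocol 6.4.5 also holds the dose at unscheduled visits.

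| Week 4 visit | d | Displacing gaps among 2–6, escalation at visit | Same, escalation not before Day 29 |
|---|---|---|---|
| Day 26 | −3 | 2–6 (5) | 4–6 (3) |
| Day 27 | −2 | 2–4 (3) | 3–4 (2) |
| Day 28 | −1 | 2 (1) | 2 (1) |
| Days 29–32 | 0 to +3 | none | none |
| Total of 7 × 5 = 35 | | 9 (26%) | 6 (17%) |

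Three cases in each column are ties (g = 2|d|). Week 8 is identical, shifted by 28 days.

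**4. Sensitivity to the assumed gap.** Gaps of 2–4 days give 7 of 21 (33%), or 4 of 21 (19%) with the later escalation. Gaps of 3–5 days give 5 of 21 (24%) with escalation at the visit. By turnaround of 0, 1, 2 and 3 days, the counts with escalation at the visit are 5, 4, 3 and 2 of 14.

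**5. Missing scheduled sample.** SAP 7.2 excludes hemolyzed results from analysis. If the scheduled value is missing or excluded, the nearest remaining record in the window is used, which may be a redraw as late as Day 42 or Day 70.

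**6. Which outputs use the selected value.**
- Not affected: treatment-emergent adverse events (by onset date, SAP 7.1.5), maximum postbaseline grade (all records, SAP 3.7.2 and 7.2.2.2), liver-criteria counts (all postbaseline visits, SAP 7.2.3) and listings.
- Already dropped: numeric laboratory summaries (SAP 7.2.1).
- Open to the effect: categorical laboratory data by visit (SAP 7.2.2.2), and any by-visit summary of Child-Pugh/MELD, liver biochemistry, FGF19/C4 or other biomarkers. Some of the relevant sections are redacted.

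**The case against.** The case for leaving the rule alone is substantial.

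- **The visible primary safety analyses do not use it.** A reader might infer that abnormal 30 or 60 mg results vanish from the safety evaluation. They do not: step 6 shows that grades, liver criteria and listings keep every record. This stands.
- **No visible table is labelled by dose.** The SAP labels results by visit, and the protocol summarises its safety data overall. A reader might infer that the SAP reports a 60 mg value as a 30 mg result. Reading Week 4 as 30 mg follows from the protocol's staged design, not from an SAP table. This stands as a limit on the claim.
- **The fractions are not rates.** A reader might take 26% as the share of visit values affected. It is conditional on a repeat having occurred and weights all visit days and gaps equally. For scale only: Protocol 1.5 reports Grade 3 or 4 ALT elevation in 6 of 154 cilofexor subjects in other populations. Applied to 20 planned subjects that is 20 × 6/154 = 0.78 subjects, and 0.78 × 9/35 = 0.20. Repeat triggers differ, so this is an illustration, not an estimate.
- **Escalation at an early visit is not certain.** It depends on tolerability (Protocol 3.1), and Protocol 3.2 has it after 4 weeks on each dose. The protocol does not settle whether a Day 26 visit brings escalation that day, and those passages should be reconciled. Waiting until the nominal day lowers the count to 6 of 35 but does not remove it.
- **Repeat-driven substitution does not reach everything in Table 3-1.** Visible repeat rules cover laboratory tests and Child-Pugh only (MELD is computed from laboratory values). None triggers repeat pruritus scores or other biomarkers. This stands.
- **The displacing record is at most 6 days into the new dose** (Day 26 to Day 32). The documents give no figure for how far a value moves in that time, so the size of any shift is unknown.

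None of these points supplies a rule that keeps a post-escalation record out of the earlier visit.

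**Conclusion.** The point holds in a limited form. Each window runs 13 days past the nominal escalation day, and the selection rule takes no account of dose. Displacing an existing end-of-stage sample needs three things: a visit 1 to 3 days early, a repeat close behind it, and a subject who has escalated. Given a repeat at 2 to 6 days, that is 9 of 35 combinations, or 6 of 35 under later escalation, resting on equal weights and an assumed turnaround. Where the scheduled sample is missing or hemolyzed, the visit need not have been early. Subjects who do not escalate are unaffected.

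The consequence is confined to by-visit single-value summaries, and its reach in redacted sections cannot be checked. The documents do not support reading this as a flaw in the adverse-event, toxicity-grade or liver-criteria results. It is worth correcting because the error is selective and the correction is cheap.

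**What to change.** Add to SAP 3.7.2/3.7.3: for Week 4 and Week 8, and their post-interruption counterparts, only records collected before the first dose of the next dose level are eligible, including the predose sample on that day. Apply the nearest-day and tie rules among eligible records only. List records taken shortly after escalation as unscheduled instead of assigning them to the earlier visit; they still count toward maximum grade.

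Two details for programming. A subject who never receives the next level keeps all records in the window. For post-interruption visits, the comparison date must be the first post-interruption dose at that level, since a re-challenged subject may already have taken that level before the interruption.

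This has precedent in SAP 3.7.3: baseline is limited to records on or before the first dose, FGF19/C4 uses the predose value by visit, and a FibroScan value from a different probe is set to missing.

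The cost is one sentence and one date comparison, using dosing dates from the study drug administration eCRF (Protocol 8.5.1). A few visit values become missing when the only sample was taken after escalation.
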